4.2 SCIENTIFIC RATIONALE FOR STUDY DESIGN

As this is the first study utilizing UPA for this indication, a pilot feasibility study is warranted to ensure that patients are willing to take part in a research study of this kind, be adherent to the study protocol, monitor the effectiveness of the study medication for this use, and evaluate for any possible side effects or adverse events. As such, we will be employing a convenience sample of patients presenting with early pregnancy loss. No comparison group will be utilized.

4.3 JUSTIFICATION FOR DOSE

UPA 90mg will be utilized for this study based on multiple factors. As this is the first use of UPA for this indication, no prior dosage data is available. Safety of UPA has been well-documented at dosages over 90mg, both from the FDA package insert that notes a lack of adverse events at dosages up to four times the standard dose of UPA (thus up to 120mg) as well as from phase 1 dose determination studies that showed that a single dose of UPA up to 100mg was well tolerated [16, 28]. Further, similar endometrial changes have been noted between UPA 100mg and mifepristone 200mg, suggesting that UPA may be effective at a dose of approximately one half that of mifepristone [19]. In clinical practice, when mifepristone is used for emergency contraception, which is the FDA-approved indication for UPA, mifepristone most effective at doses of 25-50mg compared to UPA 30mg [29], again suggesting that mifepristone may be effective at between one to two times the dosage of UPA. Lastly, UPA 90mg was the dosage used when UPA was studied in place of mifepristone 200mg for cervical preparation prior to dilation and evacuation for termination of pregnancy between 16- and 18-weeks' gestation [23, https://clinicaltrials.gov/ct2/show/NCT03802149]. We further wanted a dosage of UPA that would be easily accessible based on the current packaging of UPA, which is in 30mg tablets for ease of use among participants. Given that mifepristone 200mg is used in early pregnancy loss, we propose a dose of UPA 90mg for this study. No dose adjustments will be made for UPA, although further study could examine the effectiveness of a lower dosage of UPA on pregnancy expulsion.

4.4 END OF STUDY DEFINITION

A participant is considered to have completed the study if he or she has completed all phases of the study including the last visit or the last scheduled procedure shown in the Schedule of Activities (SoA), Section 1.3.

The end of the study is defined as completion of the last visit or procedure shown in the SoA in the trial globally.

5 STUDY POPULATION

5.1 INCLUSION CRITERIA

To be eligible to participate in this study, an individual must meet all of the following criteria:

- 1. Provision of signed and dated informed consent form
- Stated willingness to comply with all study procedures and availability for the duration of the study
- 3. English or Spanish-speaking
- 4. Female, age 18 years or older
- 5. Ultrasound examination showing a non-viable intrauterine pregnancy between 5- and 12-weeks' gestation as indicated by the Doubilet criteria or anembryonic gestation [5], see Appendix A

5.2 EXCLUSION CRITERIA

An individual who meets any of the following criteria will be excluded from participation in this study:

- 1. Desire for non-medical management of early pregnancy loss (either expectant management or surgical management)
- 2. Hemodynamically unstable
- 3. Women with incomplete or inevitable abortion (due to high efficacy of misoprostol alone)
- 4. Contraindication or allergy to ulipristal acetate or misoprostol (glaucoma, mitral stenosis, sickle cell anemia, chronic glucocorticoid use)
- 5. Evidence of a viable intrauterine pregnancy, ectopic pregnancy, or pregnancy with IUD in place
- 6. Evidence of pelvic infection
- 7. Hemoglobin <9.5g/dL
- 8. Known cardiovascular disease (arrhythmia, cardiac failure, valvular disease, angina)
- 9. Known clotting or bleeding disorder, or on anticoagulation therapy
- 10. Use of the following medications that may influence metabolization of the study medications: barbituates, bosentan, carbamazepine, felbamate, griseofulvin, oxcarbazepine, phenytoin, rifampin, St. John's Wort, topiramate [16]
- 11. Use of CYP3A4 inhibitors within five elimination half-lives of ulipristal acetate
- 12. Chronic adrenal failure (risk of acute renal insufficiency)
- 13. Concurrent long-term corticosteroid therapy (risk of acute renal insufficiency)
- 14. Any history of underlying liver disorder, including hepatitis
- 15. Elevation of any or all liver enzymes (ALT, AST, total bilirubin) above the upper limit of normal (ULN) at baseline testing prior to enrollment
- 16. A family history of hepatitis or currently living with a person who has been given a diagnosis of hepatitis
- 17. A history of or currently working as a sex worker
- 18. A history of or currently using intravenous (IV) drugs
- 19. A self-reported history of alcohol dependency or abuse

Of note, exclusion criteria 1 and 2 will be evaluated by the OBGYN provider assessing the patient for EPL. No discussion of options for management of EPL will take place by the research team prior to inclusion in the study to avoid any potential bias towards medical management if the patient desires expectant or surgical management.

5.3 LIFESTYLE CONSIDERATIONS

During this study, participants are asked to:

 Abstain from intercourse until expulsion of gestational sac is noted via transvaginal ultrasonography

5.4 SCREEN FAILURES

Screen failures are defined as participants who consent to participate in the study but are not administered the study intervention (ulipristal acetate) due to either participant withdrawal from the study or change in exclusion criteria following informed consent. A minimal set of information will be kept on all screen failure participants including eligibility screening checklist, informed consent documentation, demographic questionnaire (if completed), screen failure details and any severe adverse event (SAE). This information may be used in study reports, published materials, or to respond to regulatory authorities.

Additionally, a minimal set of information will be kept for patients screened for enrollment who do not meet eligibility criteria or who do not consent to participate in the study on the study screening register.

This information includes name, date of birth, referring physician, date of referral, date of contact with patient, and patient outcome (e.g. screen out, decline to participate, enroll in study). Following completion of enrollment of study participants, this information will be de-identified with just the number of patients in each outcome (screen out, decline to participate, enroll in study) for use in study reports, published materials, or to respond to regulatory authorities.

5.5 STRATEGIES FOR RECRUITMENT AND RETENTION

We propose a convenience sample as this is a pilot feasibility study. We propose enrolling 40 patients in the study based on an average of two patients presenting with early pregnancy loss per week at viability ultrasounds at UNC Chapel Hill OBGYN clinics over a year of recruitment. We estimate that 100 patients will be diagnosed with EPL to enroll these 40 patients given prior recruitment rates from studying mifepristone and misoprostol for early pregnancy loss (800 EPL patients for a total of 300 participants) [2].

This will be a single site study at UNC Chapel Hill. Participants will be recruited from OBGYN clinics at their viability scan upon diagnosis of EPL. Recruitment will take place at UNC Chapel Hill OBGYN clinics and UNC Chapel Hill Emergency Department. To aid providers in recruitment efforts, the study coordinator and principal investigator will pre-screen patient visits at the UNC Chapel Hill OBGYN clinics to identify those patients presenting for an early pregnancy ultrasound based on their visit type. Providers at the UNC Chapel Hill OBGYN clinics will be notified via secure EPIC message which of their patients may be eligible for recruitment to the study if they are diagnosed with an early pregnancy loss on that ultrasound. No additional patient information will be obtained until after a diagnosis of early pregnancy loss has been confirmed and the patient has been referred to the study team from the primary medical team.

Once early pregnancy loss has been diagnosed on ultrasound, patients are referred back to their primary OBGYN provider for counseling on the diagnosis and discussion of management options, often on the same day as the ultrasound. Patients desiring medical management of EPL are referred to the GYN consultation team at UNC via a telephone call for more information regarding medical management and prescription of the requisite medications. The GYN consultation team will offer patients the standard of care of mifepristone and misoprostol versus admission into the study for ulipristal acetate and misoprostol. Patients interested in the study will then be approached by the research staff. Patients who initially elect for expectant management of their early pregnancy loss but desire medical management at a later date may be offered admission into the study as well within the first two weeks following diagnosis, as over 50% of patients will pass their pregnancy after two weeks following diagnosis [27].

Thus, patients approached for participation will meet the following criteria:

- Diagnosed with early pregnancy loss or anembryonic gestation between 5- and 12-weeks' gestation on viability ultrasound at UNC Chapel Hill OBGYN clinics and UNC Chapel Hill Emergency Department
- Desire medical management of early pregnancy loss and are clinically stable to do so (not hemodynamically unstable or with active vaginal bleeding)
- Interested in learning more about the study from research team

To aid in recruitment efforts, flyers will be placed in each of the two recruitment locations and brochures will be offered to patients if they are considering admission to the study but need time to process their diagnosis. All flyers and brochures will have contact information for the study team so

patients can reach out to the research team directly. Provider flyers will also be placed in the provider workspaces at both recruitment locations and in the GYN workspace at UNC Chapel Hill where the GYN consultation team is based to provide detailed information on the study and eligibility requirements. All study materials will be written to an appropriate reading level to ensure comprehension among all potential participants.

All counseling on the diagnosis of early pregnancy loss and options for management of early pregnancy loss will take place prior to patient being approached by the research staff. Research staff will reach out to potential participants via telephone call to schedule an eligibility screening at the UNC Same Day Clinic. Research staff will then assess patients for study eligibility and proceed with study activities if the patients are eligible for participation.

Participants will enroll in the study once they are screened for inclusion and exclusion criteria from the study team and the study team has been able to review laboratory tests (hemoglobin, hepatic function tests) to ensure the patient is an appropriate candidate for enrollment. Patients will be offered enrollment into the study and then complete their baseline visit including the demographic questionnaire and administration of UPA.

Spanish-speaking patients make up a key demographic seeking OBGYN care at UNC Chapel Hill, with approximately 10% of individuals identifying as Latinx in the surrounding catchment area. As such, we will include Spanish speaking patients within our study population. All consent and data collection forms will be translated into Spanish for use with this patient population. Additionally, all patient interactions will take place with a Spanish-certified research staff member or with a certified Spanish interpreter (either in person or via telephone).

All women recruited to the study will be pregnant but have already been diagnosed with an early pregnancy loss and thus do not have any risks to an ongoing pregnancy by participating in the study. Participants will be offered psychological support for their loss as part of their standard care for early pregnancy loss. No other vulnerable patients will be included in the patient population including minors under 18 years of age, prisoners, or patients unable to provide informed consent.

UNC-Chapel Hill students and employees may seek OBGYN care at UNC-Chapel Hill and will not be excluded from the study. Any information regarding medical care for UNC-Chapel Hill students or employees will be documented appropriately in their medical charts, which are confidential from UNC-Chapel Hill faculty or employers. Additionally, as with all other patients, all research materials relating to the study will be kept confidential and will not be shared with UNC-Chapel Hill faculty or employers.

As part of the study, participants will receive compensated medical care for management of their EPL including no cost medication for the study intervention and follow up visit with transvaginal ultrasound to confirm resolution of the pregnancy. Subjects will also receive a gift card of USD \$20 for their travel and time to their follow up visit(s) on day 3 and day 8, as often outside the context of this study these follow ups are completed via phone call. They will also receive parking vouchers to park at the UNC Chapel Hill campus for follow up. As this reimbursement is nominal, the risk for coercion is low. Further, all study procedures are in line with the standard of care for treatment of EPL at UNC such that patients do not risk receiving different care by completing the study.

6 STUDY INTERVENTION

6.1 STUDY INTERVENTION(S) ADMINISTRATION

6.1.1 STUDY INTERVENTION DESCRIPTION

The study intervention will involve administration of 90mg UPA (three 30mg oral tablets) followed by 800mcg misoprostol (four 200mcg tablets) vaginally 6 to 18 hours after.

- Information regarding UPA 30mg oral tablet is detailed in the full prescribing information from the FDA. Use of UPA for this purpose is being studied under an IND (pending).
- Information regarding misoprostol 200mcg tablet is detailed in the full prescribing information
 from the FDA. While the FDA approves misoprostol for treatment of gastric ulcers, the dose and
 route of 800mcg misoprostol vaginally for medication abortion or medication treatment of early
 pregnancy loss has been studied extensively and is the most successful regimen to date [30, 31].

6.1.2 DOSING AND ADMINISTRATION

Participants will be given 90mg UPA (three 30mg oral tablets) in the presence of research staff on baseline/enrollment visit 1 (day 0) after determining eligibility and giving informed consent. Patients will be prescribed 800mcg misoprostol (four 200mcg tablets) and instructed to self-administer misoprostol vaginally 6 to 18 hours after administration of UPA. Participants will be given oral medications to manage pain and symptoms during their EPL from their OBGYN provider prior to discharge home.

Medication timing of misoprostol administration will be based on post-hoc analysis of misoprostol administration following mifepristone for early pregnancy loss. These data suggest that patients have the highest likelihood of success when misoprostol is administered 7 to 20 hours after mifepristone [32]. Pharmacokinetic data suggest that peak concentrations of ulipristal acetate and its active metabolite are 0.9 hours and 1 hour respectively, compared to mifepristone that reaches peak concentrations after 90 minutes; thus we propose earlier times when compared with those recommended with mifepristone [16,17]. Further, extensive data has studied vaginal misoprostol 6 hours after mifepristone for medication abortion with good success [33].

If a gestational sac is still present on transvaginal ultrasound on visit 2 (day 3), expectant management, medical management or surgical management will be offered to patients. Patients desiring additional medical management will be instructed to administer 800mcg misoprostol vaginally or buccally within 24 hours of their appointment. Patients may not be eligible for additional dosage of misoprostol if they are hemodynamically unstable and necessitate urgent or emergent surgical intervention.

6.2 PREPARATION/HANDLING/STORAGE/ACCOUNTABILITY

6.2.1 ACQUISITION AND ACCOUNTABILITY

UPA 90mg will be dispensed by study coordinators at visit 1. Prescription for misoprostol will be sent to the UNC Chapel Hill pharmacy for patients to pick up prior to discharge.

6.2.2 FORMULATION, APPEARANCE, PACKAGING, AND LABELING

UPA tablets are supplied as 30mg white, round, curved tablets marked with "ella" on both sides. Three tablets will be administered to patients at one time. UPA is manufactured by Osny Pharma in France and is under license from Laboratoire HRA Pharma. UPA is distributed by Watson Pharma, Inc [16].

6.2.3 PRODUCT STORAGE AND STABILITY

UPA tablets are supplied in a PVC-PE-PVDC-aluminum blister. The medication should be stored at 68-77 degrees F and the blisters will be kept in the outer carton to protect from light [16].

6.2.4 PREPARATION

No further preparation of UPA is needed for the study intervention.

6.3 MEASURES TO MINIMIZE BIAS: RANDOMIZATION AND BLINDING

As UPA has not been studied for this indication, we propose a pilot study without randomization or blinding to assess the feasibility and effectiveness of this intervention. Once feasibility has been demonstrated, a subsequent randomized controlled trial may be undertaken.

6.4 STUDY INTERVENTION COMPLIANCE

Patients will take UPA in the presence of study staff prior to discharge from visit 1. Participants will report the time that they self-administered misoprostol vaginally on their return for their day 3 transvaginal ultrasound.

6.5 CONCOMITANT THERAPY

For this protocol, a prescription medication is defined as a medication that can be prescribed only by a properly authorized/licensed clinician. Patients will be advised to not take certain medications that affect CYP450 metabolism pathways as detailed in exclusion criteria (5.2) as these medications may influence metabolism of UPA. Otherwise, no recording of concomitant medication therapy will be collected from patients.

6.5.1 RESCUE MEDICINE

Not applicable.

7 STUDY INTERVENTION DISCONTINUATION AND PARTICIPANT DISCONTINUATION/WITHDRAWAL

7.1 DISCONTINUATION OF STUDY INTERVENTION

Discontinuation from taking UPA will constitute discontinuation from the study protocol and participants may receive any option of EPL management (expectant management, medical management, or surgical management) from their OBGYN. If a clinically significant finding is identified (including, but not limited to changes from baseline) after enrollment but before UPA administration, the investigator or qualified designee will evaluate if any change in participant management is needed. Any new clinically relevant finding will be reported as an adverse event (AE).

7.2 PARTICIPANT DISCONTINUATION/WITHDRAWAL FROM THE STUDY

Participants are free to withdraw from participation in the study at any time upon request. An investigator may discontinue or withdraw a participant from the study for the following reasons:

Significant study intervention non-compliance

- If any clinical adverse event (AE), laboratory abnormality, or other medical condition or situation occurs such that continued participation in the study would not be in the best interest of the participant
- If the participant meets an exclusion criterion (either newly developed or not previously recognized) that precludes further study participation
- Participant presents for enrollment >2 weeks following diagnosis of early pregnancy loss as over 50% of participants will have complete miscarriage with expectant management alone at this time point [27].

The reason for participant discontinuation or withdrawal from the study will be recorded on the Case Report Form (CRF). Subjects who sign the informed consent form but do not receive the study intervention may be replaced.

Participants who discontinue or withdraw from the study will not be replaced. Instead, additional enrollment will commence to reach the targeted sample size of 40 study participants.

7.3 LOST TO FOLLOW-UP

A participant will be considered lost to follow-up if he or she fails to return for 2 scheduled visits and is unable to be contacted by the study site staff.

The following actions must be taken if a participant fails to return to the clinic for a required study visit:

- The site will attempt to contact the participant and reschedule the missed visit within 1 day and counsel the participant on the importance of maintaining the assigned visit schedule and ascertain if the participant wishes to and/or should continue in the study.
- Before a participant is deemed lost to follow-up, the investigator or designee will make every
 effort to regain contact with the participant (where possible, 3 telephone calls and, if necessary,
 a certified letter to the participant's last known mailing address or local equivalent methods).
 These contact attempts should be documented in the participant's medical record or study file.
- Should the participant continue to be unreachable, she will be considered to have withdrawn from the study with a primary reason of lost to follow-up.

Similarly, the following actions will be taken if a participant fails to return for her laboratory visit (Day 14 ± 1 day):

- The site will attempt to contact the participant and reschedule the laboratory visit within 1 day and counsel the participant on the importance of maintaining the laboratory visit and ascertain if the participant wishes to and/or should continue in the study.
- Before a participant is deemed lost to follow-up, the investigator or designee will make every
 effort to regain contact with the participant (where possible, 3 telephone calls and, if necessary,
 a certified letter to the participant's last known mailing address or local equivalent methods).
 These contact attempts should be documented in the participant's medical record or study file.
- Should the participant continue to be unreachable, she will be considered to have withdrawn from the study with a primary reason of lost to follow-up.

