Follow up of medical management of EPL generally consists of confirmation of pregnancy expulsion by ultrasound examination or serial beta-hCG measurements in settings where ultrasound is not available [1]. There is no standard of care regarding specific intervals when ultrasonography or laboratory follow up assessment should take place. Study follow up schema for our study is based on participant follow up design from a similar study of mifepristone and misoprostol for EPL [2].

Participants will follow up with the UNC Family Planning Division for a transvaginal ultrasound on study day 3 to ensure expulsion of the gestational sac. Women generally experience cramping and vaginal bleeding 1 to 4 hours following misoprostol administration and pass their pregnancy within 24 hours of starting to bleed. Thus, follow up on day 3 will assess participants who are able to pass their pregnancy with a single dose of UPA and misoprostol.

For those who still have a pregnancy in the uterus, they will be offered an additional dose of 800mcg misoprostol, expectant management, or surgical management. Those who did not have expulsion of the pregnancy on day 3 and elect for an additional dose of misoprostol or expectant management will follow up with the UNC Family Planning Division for another transvaginal ultrasound on study day 8 to ensure expulsion of the gestational sac. As some studies of EPL assess for response 7 days after medication administration, we will be able to compare our data to similar studies through our day 8 follow up results [3]. Further, twenty-five to thirty percent of EPL will pass with expectant management alone one week after diagnosis [27].

Participants will be assessed for possible liver toxicity on study day 14 through a laboratory test of ALT, AST and total bilirubin.

All study participants will receive a phone call on study day 30 to what additional treatment patients needed for their early pregnancy loss, investigate any side effects or adverse events, and identify acceptability of the treatment. Most symptoms of bleeding and abdominal cramping following medical management of EPL occur in the first two to four weeks following medication administration; thus, 30 days is an adequate time to assess for side effects and acceptability of treatment while not being too remote from the time of the pregnancy passing.

A detailed description of all study visits is provided below:

Visit 1 (Day 0):

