9.4.2 ANALYSIS OF THE PRIMARY FEASIBILITY OUTCOME VARIABLE(S)

- Recruitment (%): number of participants in study/number of patients screened for participation
- Adherence (%): number of participants adhering to study intervention (UPA + misoprostol vaginally after 6 to 18 hours)/number of participants in study
- Retention (%): number of participants attending all study visits (day 0, 3/8, 30)/number of participants in study

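### Section 7.3 defines loss to follow-up by two missed visits, but its action lists close out an unreachable woman after one, so a missed Day 14 lab can end follow-up before the Day 30 call that retention counts

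*Combined protocol and SAP*

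**What the plan says.** Section 7.3 opens with a definition that has two conditions. A participant is "considered lost to follow-up if he or she fails to return for 2 scheduled visits and is unable to be contacted" by site staff.

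Two action lists follow. The first begins: "The following actions must be taken if a participant fails to return to the clinic for a required study visit". The second says that "the following actions will be taken if a participant fails to return for her laboratory visit". Each asks for a rescheduling attempt within 1 day and then further effort to reach her ("where possible, 3 telephone calls and, if necessary", a certified letter). Neither sets a time limit on that effort. Both end the same way for a woman who still cannot be reached: "she will be considered to have withdrawn from the study with a primary reason of lost to follow-up". Neither refers to a second missed visit or to Day 30.

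Other sections treat the Day 30 contact as universal. Section 4.1 states: "All study participants will receive a phone call on study day 30". The visit descriptions in 4.1 have all participants completing Visit 4, and Section 8.1 again gives the call to all patients. Section 9.4.2 scores retention, a primary feasibility outcome, as "number of participants attending all study visits (day 0, 3/8, 30)/number of participants in study". Section 9.1 sets the expectation above 90%. The Day 14 lab is not in the retention numerator.

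**The concern.** One section gives two answers to when follow-up stops. The definition needs two missed visits. The lists can be read as needing one, and the lab list was written for a draw that happens only once. If site staff follow the lab list to its last step, a woman can be recorded as withdrawn because of a contact that retention does not count, and so never receive the contact that it does count.

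Two things are at stake. The first is the retention figure, which would depend on which sentence of 7.3 the staff applied. The second is the Day 30 information. The schedule of activities places the additional-treatment and acceptability questionnaires only at Visit 4, and Section 8.3.4 places the solicited questions on bleeding and infection in that call. A woman closed out through the lab list also has no post-treatment liver result unless the draw was rescheduled.

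**Working it through.** The plan states no loss or retention calculation to reproduce, and Section 9.2 says that no formal power calculation is required. The check is a comparison of texts, followed by an illustration of scale.

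**1. The two rules in 7.3**

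| | Definition | Action lists |
|---|---|---|
| Missed visits needed | 2 scheduled visits | 1 required clinic visit, or the Day 14 lab |
| Must also be unreachable | Yes | Yes, after the contact attempts |
| Says the Day 30 call is still attempted | No | No |

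Both rules require failed contact. The difference is one missed visit against two.

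**2. Timing.** A woman with no sac at Visit 2 does not need Visit 3. After attending Day 3, her remaining contacts are the lab (14 ± 1, so to Day 15) and the call (30 ± 7, so Day 23 to Day 37). She cannot have missed two contacts until the Day 30 call is missed. The lab list can be completed at any time after Day 15, and 23 − 15 = 8 days pass before the call window opens.

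**3. Who changes retention status**

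| Pattern | Two-visit rule | One-visit reading |
|---|---|---|
| Misses a required Day 3 or Day 8 visit, not rescheduled | Not retained | Not retained |
| Attends Day 3/8, misses lab, then reached | Day 30 decides | Day 30 decides |
| Attends Day 3/8, misses lab, unreachable then and at Day 30 | Not retained | Not retained |
| Attends Day 3/8, misses lab, unreachable then, would answer at Day 30 | Retained | Not retained if closed out before the call |

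Only the last row differs.

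**4. Margin.** With the target of 40 (Section 7.2), 36/40 = 90.0%, which is not above 90%, and 37/40 = 92.5%. So 37 are needed and 40 − 37 = 3 can be lost. Each close-out costs 1/40 = 2.5 percentage points.

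**5. Illustration on assumed rates.** Let p be true retention on Days 0, 3/8 and 30 if every call is attempted. Let q be the share of those otherwise retained women who fall in the last row and are closed out. Retention becomes r = p(1 − q), and the chance of at least 37 is P(X ≥ 37) with X ~ Binomial(40, r). The documents give neither p nor q. Women who would not answer at Day 30 fail under both rules and are already within 1 − p.

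| q | r at p = 0.97 | P(X ≥ 37) | r at p = 0.95 | P(X ≥ 37) |
|---|---|---|---|---|
| 0 | 0.970 | 0.969 | 0.950 | 0.862 |
| 2.5% | 0.946 | 0.830 | 0.926 | 0.659 |
| 5% | 0.922 | 0.615 | 0.903 | 0.444 |
| 7.5% | 0.897 | 0.401 | 0.879 | 0.269 |

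At p = 0.97, q = 2.5% is 40 × 0.97 × 0.025 = 0.97, about one woman. At q = 7.5% it is about three.

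**6. Other Day 30 data.** Side effects are also collected at Days 3 and 8, and adverse events treated at the site are abstracted from the chart (8.1, 8.3.5). The main secondary analysis in 9.3 keeps only adherent completers, so a lab-only close-out shrinks that set. It also removes Day 30 answers from the sensitivity analysis of all enrolled women with data.

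**The case against.** A consistent reading of 7.3 exists. The first sentence defines loss to follow-up, and the lists describe what staff do next. The step on effort before a woman is deemed lost can be taken as pointing back to that definition. No passage cancels the Day 30 call for an unreachable woman, and three places give it to everyone. With no deadline on the contact attempts, they could run past Day 23 into the call window. This stands as a reason to call the text unresolved rather than plainly contrary to 4.1. It does not remove the problem, because the last step of each list assigns the status without the two-visit condition.

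A reader might infer three stronger things, and the documents support none of them:

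- **That one missed visit alone withdraws a woman.** It does not. She must also stay unreachable after the rescheduling attempt, the calls and, if necessary, the letter.
- **That every 30-day outcome is lost.** Adverse events are partly covered by the Day 3/8 reports and the chart. Mainly at risk are acceptability, self-reported additional treatment and the solicited Day 30 questions.
- **That the two-visit rule always protects Day 30.** It does not. Missing Day 3 and a required Day 8, or Day 3 and the lab if that counts as a scheduled visit, can meet it earlier.

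It is also fair that the 90% figure is an expectation, with no formal testing (9.4.1) and no decision rule attached. Section 7.2 adds enrolment after withdrawals to reach 40, so the retention denominator under early close-out is itself unclear. The probabilities above hold it at 40.

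**Conclusion.** The point holds as an internal conflict that the text does not settle. Section 7.3 can be applied with a one-visit or a two-visit trigger. On the literal one-visit reading, a woman who attended Day 3 (and Day 8 if required), missed only the Day 14 lab and could not be reached then may be closed out before Day 30.

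The effect on retention is confined to that group. Its size is unknown, because the documents give no rate of missed labs or failed contact. What is certain is the narrow margin: with 40 women, three losses still pass and a fourth does not. The illustration shows that one to three such close-outs on average would noticeably lower the chance of exceeding 90%. It rests on the assumed values of p and q, independent outcomes and a fixed denominator of 40. It is not a forecast.

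**What to change.** Reconcile 7.3 to a single lost-to-follow-up rule, in four parts:

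1. State that a missed clinic or lab visit triggers the contact attempts but does not by itself cancel later contacts.
2. Remove or reword the last step of both lists so that it no longer assigns withdrawal after one missed visit.
3. Attempt the Day 30 call for every woman given UPA who has not withdrawn consent.
4. Assign lost-to-follow-up status for the retention count only once the Day 30 window has closed (30 + 7 = Day 37).

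The cost is a wording change in one section and a few extra phone calls. The sample size, visit schedule and analysis stay as they are.
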